After enrolling 400 patients (37.7% of total enrollment) a BLINDED interim analysis will be conducted by the independent DSMB as follows. For each subject the DSMB will be provided with 1) the subject ID number, 2) whether or not the primary endpoint (post-ERCP pancreatitis) occurred, 3) whether or not a bleeding event occurred, and 4) in which group (high-dose or standard dose regimen) the patient belonged. If $> 66\%$ of the pancreatitis cases or bleeding cases are in a particular group (high-dose or standard dose regimen), the DSMB will break the code to determine whether these events are in the standard 100 mg indomethacin group or high-dose indomethacin group. This value was selected because it represents a 2:1 (double) frequency of an endpoint outcome in one group or another. If either of these events has occurred at this high frequency in one group or another, then the DSMB will decide that the study should be stopped. Even if the DSMB is required to break the code for this above listed purpose, the investigators will never be aware of this information. The DSMB will simply tell the investigators whether or not to continue the study. If during this blinded interim analysis, the DSMB finds that the proportion of the patients with pancreatitis in the higher dose indomethacin group is significantly lower, a formal statistical analysis will be performed and statistical significance will only be declared (and the study terminated) if the two-sided p value is less than 0.005. In this unlikely circumstance, the DSMB will inform the investigators that the study should be terminated for ethical reasons (i.e., it would be unethical to withhold this from high-risk patients).

After enrolling 600 subjects (56.6% of total enrollment) a BLINDED interim analysis will be conducted by the independent DSMB as follows. For each subject the DSMB will be provided with 1) the subject ID number, 2) whether or not the primary endpoint (post-ERCP pancreatitis) occurred, 3) whether or not a bleeding event occurred, and 4) in which group (high-dose or standard dose regimen) the patient belonged. This analysis will be performed because it was a specific request of the DSMB that it be performed to ensure the safety of subjects. Analysis and criteria for stopping the study at this second interim analysis will be the same as those noted above, for the first interim analysis.

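### Section F's two interim rules give opposite instructions for a favourable pancreatitis split above 66% with p from 0.005 to 0.05, so Section D's power of 0.8 depends on which rule governs

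*Combined protocol and SAP*

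**What the plan says.** Section F (Statistical analysis) describes a DSMB look after 400 patients and applies the same criteria again after 600.

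**The 66% rule.** If more than 66% "of the pancreatitis cases or bleeding cases are in a particular group", the code is broken "to determine whether these events are in the standard 100 mg indomethacin group or high-dose indomethacin group". The cutoff is explained: "This value was selected because it represents a 2:1 (double) frequency of an endpoint outcome in one group or another". The condition for stopping names both groups: "If either of these events has occurred at this high frequency in one group or another". The consequence is mandatory: "then the DSMB will decide that the study should be stopped". No significance condition is attached.

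**The 0.005 rule.** This applies if the DSMB sees that the pancreatitis rate "in the higher dose indomethacin group is significantly lower, a formal statistical analysis will be performed". A strict level is then set for that analysis: "statistical significance will only be declared (and the study terminated) if the two-sided p value is less than 0.005". The plan expects this to be rare: "In this unlikely circumstance, the DSMB will inform the investigators that the study should be terminated for ethical reasons".

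The opening of Section F sets the primary test as a two-tailed Fisher's exact test at two-sided p<0.05. Section D gives 1036 patients for 9.2% against 4.6% with power 0.8 and mentions no interim looks. Section E says only that recruitment may end if interim analyses suggest it.

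**The concern.** For pancreatitis in favour of high dose, the two rules overlap. Take a split with more than 66% of cases in the standard arm that is significant at 0.05 but not at 0.005. The 66% rule ends the study; the 0.005 rule does not. The DSMB cannot follow both.

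The overlap is not a remote corner. The cutoff is a doubling, and the effect the trial is designed to detect is a halving. If the hypothesis is true, the trial is expected to sit on the cutoff.

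Two further gaps matter. The plan does not say how a trial ended by the 66% rule is tested: the interim text gives only the 0.005 criterion, while the p<0.05 test at the start of Section F is not limited to full enrolment. And the 66% rule covers bleeding with no direction and no minimum count, so a single event, being 100% in one group, meets it.

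At stake are a clear instruction to the DSMB and the meaning of the stated power.

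**Working it through.** **Inputs.** Pancreatitis 9.2% and 4.6%, two-sided alpha 0.05, power 0.8, total 1036 (Section D); looks at 400 and 600, the 66% and 0.005 rules, Fisher's exact test (Section F). Allocation is not stated. I assume 1:1, which equating 66% of cases with a 2:1 frequency implies, and equal arms at each look: 200, 300 and 518 per arm.

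**1. The plan's own figure.** With mean rate 0.069:

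n0 = [1.960·√(2·0.069·0.931) + 0.8416·√(0.092·0.908 + 0.046·0.954)]² / 0.046² = (0.7025 + 0.3004)² / 0.002116 ≈ 475.4 per arm.

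With continuity correction: n = (n0/4)·[1 + √(1 + 4/(n0·0.046))]² = 118.85 × 2.0876² ≈ 518 per arm, or 1036. This matches Section D. Exact Fisher power at 518 per arm with no looks is 0.81.

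**2. Cutoff against planned effect.** 9.2/(9.2 + 4.6) = 66.7% of cases in the standard arm.

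**3. Example splits** near the expected totals (200 × 0.138 = 27.6 cases at 400; 300 × 0.138 = 41.4 at 600), taking significantly lower as p<0.05:

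| Look | Standard vs high | Share in standard arm | Fisher p | 66% rule | 0.005 rule |
|---|---|---|---|---|---|
| 400 | 19 vs 9 | 68% | 0.076 | stop | not reached |
| 400 | 20 vs 8 | 71% | 0.029 | stop | continue |
| 400 | 21 vs 7 | 75% | 0.0097 | stop | continue |
| 400 | 22 vs 6 | 79% | 0.0027 | stop | stop |
| 600 | 28 vs 13 | 68% | 0.022 | stop | continue |

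**4. How often.** Exact enumeration of the two binomial counts under the planned effect:

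| Share above 66% in standard arm | At 400 | At 600 (ignoring stops at 400) |
|---|---|---|
| Any p | 53.7% | 53.2% |
| p<0.005 (rules agree) | 11.7% | 23.6% |
| 0.005≤p<0.05 (direct conflict) | 25.3% | 27.2% |
| p≥0.05 (66% rule alone) | 16.7% | 2.4% |

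The chance of a direct conflict at 400, or at 600 in trials continuing past 400, is 40.2%.

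**5. Power, pancreatitis rules only.** Success is p<0.005 favouring high dose at a look, or p<0.05 favouring high dose at the end, unless stated otherwise. A p<0.005 result takes precedence over the 66% stop at the same look.

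| Reading | Power |
|---|---|
| p<0.005 is the only favourable stop (66% rule for high-dose excess only) | 0.81 |
| 66% rule also stops favourable splits with p≥0.05 | 0.65 |
| 66% rule binds both ways; interim success needs p<0.005 | 0.35 |
| 66% rule binds both ways; stopped trials tested at 0.05 | 0.67 |

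With 9.2% in both arms, the last reading has two-sided type I error 6.2%. With only the p<0.005 stop it is 0.021 + 0.020 = 4.1%.

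**6. Bleeding, for illustration.** The documents give no planning rate. I assume equal bleeding in both arms, independent of pancreatitis, from 0.5% to 5%. The range takes in the 4/295 = 1.36% and 7/307 = 2.28% that Section C reports for clinically significant bleeding in the earlier placebo-controlled indomethacin trial. By 600 patients the bleeding trigger is met by chance, in either direction, in 81% (at 0.5%) to 18% (at 5%) of trials. If both the pancreatitis and bleeding stops act only on high-dose excess, power is 0.535 to 0.751 when stopped trials succeed only at p<0.005, and 0.643 to 0.774 when they are tested at 0.05.

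**The case against.** The strongest reply is that the 66% rule is a safety rule and acts only on an excess in the high-dose arm. Much supports this. The code is broken to learn the direction, which would be pointless if both directions led to the same act. The second look was requested for safety. After the code is broken the DSMB tells the investigators whether or not to go on, which leaves room to continue. The favourable stop is called unlikely, whereas a two-way 66% rule would trigger it in over half of trials at 400 under the planned effect. And favourable results with p<0.005 virtually always exceed 66% already, so a two-way stop would leave 0.005 no role as a stopping boundary, though it could still decide whether significance is declared.

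That makes the harm-only reading plausible, and on it the pancreatitis rules cost no power. But the stopping sentence names either group and is mandatory, and no other section limits it.

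A second reply concerns what significantly lower means. I take it as the p<0.05 that opens Section F. It could instead be an informal screen, since the formal analysis comes after it. The 0.65 reading would then drop out, but the two sentences could meet on every favourable split above 66% with p≥0.005: 25.3% + 16.7% = 42.0% of trials at 400.

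Stronger conclusions are tempting. A reader might infer that the trial has only 35% power or that 1036 is wrong. The documents do not support that: 1036 reproduces, and 0.35 needs both a binding two-way stop and no test at 0.05 afterwards. A reader might infer that type I error is inflated; that arises only if stopped trials are tested at 0.05, which the interim text does not provide for. Conversely, a reader might infer that the harm-only reading secures 0.8. It does so only if the bleeding stop, set by the same sentence, does not bind.

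**Conclusion.** Wrong as written. The interim rules contradict each other at both looks, and the text does not settle which prevails. The conflict is likely when the planned effect is true: about 40% of trials, assuming 1:1 allocation and p<0.05 as the meaning of significantly lower.

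Section D's 0.8 is correct for a fixed sample. Whether it describes the trial in Section F is undetermined. The four pancreatitis-only figures are not bounds, because a binding bleeding stop lowers each of them. The size of that loss rests on assumed bleeding rates, equal arms and independence from pancreatitis, and should be read as illustration only.

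**What to change.** The sponsor and DSMB should reconcile the sentences in Section F, for both looks, and state:

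1. which rule governs when the pancreatitis excess is in the standard arm, and what significantly lower means there;
2. how, and at what significance level, a trial stopped under the 66% rule is analysed;
3. in which direction, and from what minimum number of events, the bleeding trigger applies.

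They should then restate the Section D power, and the type I error, under the rules kept, with any bleeding assumption given. The choice of stopping rule is theirs.

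The cost is revised wording in Section F and the DSMB instructions, one joint decision, and possibly a lower stated power. The reconciliation itself needs no extra patients or data.

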While all patients undergoing ERCP may benefit from the protective effect of indomethacin, the incidence of pancreatitis in high-risk patients is such that prevention of PEP in this patient population would lead to the most substantial reduction in morbidity and health care costs. Moreover, the elevated baseline risk of PEP in high-risk patients makes clinical trials in this group more feasible due to more manageable sample sizes.

Our objective is to perform a prospective, randomized, double-blind trial evaluating two different dose regimens of rectal indomethacin in the prevention of PEP. While a single 100 mg dose (the "standard" dose) is effective in high-risk patients (17), the ideal or most efficacious dose regimen is unknown. This study will determine which dose regimen of rectal indomethacin is more effective in preventing post-ERCP pancreatitis. The results will help the research team determine whether there is reason to continue this line of research or whether it would be better to focus on a different area (perhaps use of another class of drugs or a device).

D. Sample size calculation:

An internal audit of high-risk ERCPs at the four tertiary referral centers involved in this clinical trial reveals a PEP rate of approximately 10%, despite the routine use of prophylactic pancreatic duct stent placement (24-26) in appropriate patients and selective use of indomethacin. It is anticipated that the patient characteristics/demographics in this study will be very similar to that of Elmunzer et al. (17), as inclusion and exclusion criteria will be the same (see below). In that study (17), the PEP rate in patients who received indomethacin 100 mg was 9.2%. To achieve a 50% reduction in the rate of PEP (i.e. to 4.6%), with two-sided $\alpha=0.05$ and a power of 0.8, the necessary sample size is 1036. This absolute reduction in incidence

is felt to be clinically relevant and substantial enough to change existing clinical practice.

E. Methodology- Design and procedures

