This study is designed as a prospective, randomized, double-blind clinical trial. We plan on enrolling 1036 high-risk patients undergoing ERCP. These patients will be enrolled at six tertiary care hospitals in the United States: Indiana University Hospital (Indianapolis, IN), University of Michigan Medical Center (Ann Arbor, MI), Methodist Dallas Medical Center (Dallas, TX), Aurora St. Luke's Medical Center (Milwaukee, WI), the Medical University of South Carolina (Charleston, SC), and Beth Israel Deaconess Medical Center (Boston, MA). The study will be conducted after approval from the internal review committees of all participating institutions. We have been granted an IND exemption from the Food and Drug Administration for this protocol (see attached).

Patients, study personnel, and treating physicians will be blinded to study group assignment. The randomization schedule, which is stratified according to study center, will be generated centrally at the University of Michigan and distributed to the other study sites. The randomization schedule will be kept by personnel not directly involved with the study. This same personnel will be responsible for packaging the drug and placebo. Based on current annual procedure volume, it is assumed that 700 patients will be recruited by the Indiana University site, with 336 patients recruited by the other sites. These estimates are not binding, as all sites will be allowed to continue recruiting patients until the recruitment goal is met, or interim analyses suggest early study termination. The individual sites will order the indomethacin suppositories as necessary through the research coordinator at Indiana University, as determined by their recruitment rate. The exception to this is MUSC will be ordering indomethacin suppositories on their own, which will come from the same manufacturer, G and W laboratories, that all other sites are using. The glycerin suppositories will be obtained either by each institution's standard ordering procedure, or by ordering from Indiana University. If ordering from Indiana University, the suppositories will be shipped directly to each individual site.

Inclusion criteria:

The inclusion criteria are intended to select a group of patients at high-risk (approximately 10%) for post-ERCP pancreatitis. These criteria are based on patient and procedure-related risk factors that have been previously shown in multivariable analyses to confer a significantly increased risk of PEP.

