After obtaining informed consent, subjects will undergo ERCP per clinical protocol. All procedure-related clinical decisions and interventions will be dictated by the performing physician as he or she sees fit. At the end of the procedure, it will be determined by the endoscopist and research coordinator whether the patient meets inclusion criteria. If inclusion criteria are met, subjects will be randomized by concealed allocation to receive either 100 mg or 150 mg indomethacin, in the form of two or three 50 mg identical-appearing rectal suppositories. Those patients who are randomized to receive the 100 mg dose will receive an additional glycerin suppository. The suppositories will be placed while the patient is still sedated in the ERCP suite, prior to transfer to the recovery area. Four hours later (+/- 20 minutes), those patients who were randomized to the high-dose group (already received 150 mg dose) will then receive an additional 50 mg suppository while in the recovery area. At this same time point, subjects who were randomized to the standard-dose group (already received 100 mg dose) will receive a glycerin suppository in the recovery area. All participating patients, therefore, will receive a total of 4 suppositories, as summarized below:

	Immediately post-ERCP	4 hours post-ERCP
High dose	Indomethacin 150 mg (50 mg x 3)	Indomethacin 50 mg x 1
Standard dose	Indomethacin 100 mg (50 mg x 2) + glycerin x1	glycerin x 1

There will be one source of indomethacin suppositories for all six participating sites. G and W Laboratories, Inc., South Plainfield, NJ 07080 will manufacture the indomethacin suppositories. The suppositories will then be distributed by IROKO Pharmaceuticals, LLC, Philadelphia, PA 19112.

Indomethacin and glycerin suppositories will be packaged according to the randomization schedule by personnel not directly involved in the conduct or interpretation of the study. The study package for each subject will be an opaque envelope or bottle. High-dose packages will contain 2 small plastic bags: bag #1 containing 3 indomethacin suppositories and bag #2 containing 1 indomethacin suppository. Standard dose packages will contain 2 small plastic bags: bag #1 containing 2 indomethacin suppositories and 1 glycerin suppository and bag #2 containing 1 glycerin suppository. The package will be fully opaque such that the contents of cannot be discerned without opening the envelope or bottle.

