recorded on a standardized data collection form at the time of the procedure and within 5 days and 30 days after the procedure. This information will be recorded by a research coordinator. All completed data collection forms from the University of Michigan Medical Center, Methodist Dallas Medical Center, Aurora St. Luke's Medical Center, the Medical University of South Carolina, and Beth Israel Deaconess Medical Center will be faxed, emailed, or uploaded into MiShare and sent to IU. The data will be transferred by the IU study coordinator to a master excel database, housed on a password protected desktop computer in a locked research office. A second research team member from IU will perform data entry confirmation.

F. Statistical analysis

For the analysis of the primary endpoint, the difference in the proportion of patients developing post-ERCP pancreatitis between the two groups will be analyzed using a two-tailed Fisher's exact test, with a two-sided $p < 0.05$ indicating statistical significance.

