Further, we will perform a heterogeneity in treatment effects analysis on enrolled subjects according to their pre-treatment risk of post-ERCP pancreatitis, functionally assessing whether the relative treatment effect is consistent across the spectrum of study subjects' risk of post-ERCP pancreatitis. Individual subject risk scores will be calculated by assigning one point for each major inclusion criterion and 0.5 points for each minor inclusion criterion, as previously reported (17).

It is recognized that some patients may have difficulty holding their suppositories, and expulsion of the suppositories may or may not be witnessed by study personnel. All patients will be analyzed on an intent-to-treat basis, in the group to which they were randomized. However, we anticipate that this point will have little impact on study outcome, as indomethacin suppositories dissolve quickly (rather than melt slowly) and are seldom recovered in recognizable form if the patient retains the suppository for more than a few minutes (product insert, Merck & Co.). If a suppository is recovered in visible and intact form, it may be re-inserted.

G. Budget

Funding for this study has been obtained from the American College of Gastroenterology. The Clinical Research Award amount is \$34,975 which will be used for medication costs for all sites, as well as coordinator support at Indiana University.

References:

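### The primary PEP comparison is valid and meets its power target, but it leaves out the pre-specified baseline risk score; adjusting for it would be a cheap, small gain in efficiency

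*Combined protocol and SAP*

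**What the plan says.** Four parts of the combined protocol and SAP bear on this.

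- **Primary test (section F, opening paragraph).** The difference in PEP proportions "will be analyzed using a two-tailed Fisher's exact test", two-sided at 0.05, with no covariates.
- **Risk score (section F, heterogeneity of treatment effect).** "Individual subject risk scores will be calculated by assigning one point for each major inclusion criterion and 0.5 points for each minor inclusion criterion". Its only stated use is to examine whether the relative effect is constant across baseline risk.
- **Adjusted model (section F, additional secondary analysis).** A model for PEP with treatment arm and covariates drawn from a list of 24. Univariate screening against PEP decides which enter, with at most one per 10 PEP events.
- **Design (section E).** Randomization is stratified by center only. Eligibility is settled at the end of the ERCP, before randomization and before any study suppository. Under Inclusion criteria, the criteria are described as resting on risk factors that "have been previously shown in multivariable analyses to confer a significantly increased risk of PEP".

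**The concern.** The score has what one wants in an adjustment covariate. Its formula is fixed in advance, treatment cannot affect it, it needs no data-driven selection, and it costs one parameter (or a handful of strata). If it predicts PEP, adjusting for it raises power at the same type I error and corrects for whatever chance imbalance in risk it captures. Stratifying by center does not control that imbalance.

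The secondary adjusted model is a weaker safeguard. Its covariates depend on the observed outcomes, so an imbalanced predictor can be screened out, and the set being adjusted for is unknown until the data are in. What is at stake is a modest amount of precision in the main result and a cleaner adjusted estimate if the result is borderline.

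**Working it through.** **Inputs.** From section D: PEP 9.2% on standard dosing, 4.6% on the higher dose, two-sided alpha 0.05, power 0.8, and "the necessary sample size is 1036". The allocation ratio is not stated; 1:1 is assumed, giving 518 per arm. All power figures are for a single final look and ignore the interim rules.

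**1. The plan's sample size.** Mean rate 0.069, difference 0.046.

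Uncorrected n per arm = [1.960 × √(2 × 0.069 × 0.931) + 0.842 × √(0.092 × 0.908 + 0.046 × 0.954)]² / 0.046² ≈ 475.4, rounded up to 476 (952 in total).

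Continuity-corrected n = (475.4/4) × [1 + √(1 + 4/(475.4 × 0.046))]² ≈ 518, or 1036 in total. This matches the plan exactly.

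**2. The planned test.** Exact enumeration of Fisher's test at 518 per arm gives power 0.810. Its true size is 0.040 when both rates are 9.2% and 0.038 when both are 6.9%. The test is valid, somewhat conservative, and meets its target.

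**3. What the score would add.** The documents give neither the distribution of the score nor its odds ratio per point, so both are assumed. Marginal rates are held at 9.2% and 4.6%.

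- *Simulation A:* 200,000 trials per setting; scores 1/1.5/2/2.5/3/4 in 45/15/22/8/7/3% of patients; Mantel-Haenszel test by score level against an uncorrected unadjusted test (power 0.839).
- *Simulation B:* 4,000 trials per setting (Monte Carlo standard error about 0.6 points); scores 1/1.5/2/2.5/3/3.5/4 in 30/22/20/13/9/4/2%; logistic model with a linear score against unadjusted logistic and Fisher tests on the same simulated trials.

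| Odds ratio per point | A: by score | A: gain over 0.839 | B: Fisher | B: unadjusted logistic | B: with score | B: gain from score |
|---|---|---|---|---|---|---|
| 1.0 | 0.838 | −0.1 pt | 0.809 | 0.838 | 0.837 | −0.1 pt |
| 1.5 | 0.841 | +0.2 | 0.804 | 0.830 | 0.831 | +0.1 |
| 2.0 | 0.848 | +0.9 | 0.805 | 0.833 | 0.839 | +0.6 |
| 2.5 | 0.858 | +1.9 | – | – | – | – |
| 3.0 | 0.868 | +2.9 | 0.818 | 0.843 | 0.866 | +2.3 |

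Type I error of the adjusted test was 4.97% to 4.98% in A and 4.5% to 5.3% in B.

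**4. Splitting the gain.** Fisher 0.810 to uncorrected unadjusted 0.839 is +2.9 points and has nothing to do with the score. From 0.839 to the score-stratified test is −0.1 to +2.9 points. In B the variance of the standardized risk difference, relative to the unadjusted one, was 1.00, 1.00, 0.97 and 0.94 at odds ratios of 1, 1.5, 2 and 3. In patients, 1036 × [(z of adjusted power + 1.96)/(z of unadjusted power + 1.96)]² − 1036 gives about 0, 5, 26, 56 and 91 for the five rows of A.

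**5. Chance imbalance.** With a score SD of about 0.79 (distribution B), the 95% limit for the difference in mean score is 1.96 × 0.79 × √(2/518) ≈ 0.10 point (0.096 unrounded). The odds ratio would shift by a factor of 2^0.096 ≈ 1.07 or 3^0.096 ≈ 1.11. The design odds ratio is (0.046/0.954)/(0.092/0.908) ≈ 0.48.

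**6. Room in the secondary model.** Expected events are 518 × 0.092 + 518 × 0.046 ≈ 71, so the one-per-10 rule admits about 7 of the 24 listed covariates.

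**The case against.** The strongest reply is that nothing here is wrong. An unadjusted Fisher test is a legitimate primary analysis, randomization protects its type I error whatever the chance imbalance, and it reaches the stated power. That stands. A reader might infer from the unused score that the trial is underpowered or its primary test flawed; the reproduction of 1036 and the exact power of 0.81 contradict both.

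A reader might also infer a free and sizeable gain. The documents do not support that either:

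- The Inclusion criteria text speaks of individual risk factors. It does not say that an equally weighted count predicts PEP among patients already selected on them. One major criterion or two minor ones give the same score of 1, which is also the minimum, so the range is restricted.
- A clear gain appears only towards the top of the assumed range. An odds ratio of 3 per point means 3³ = 27-fold odds between scores of 1 and 4, and nothing in the documents backs that.
- About half or more of the improvement over the plan comes from leaving Fisher's test.

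Three further points stand. Chance imbalance is not ignored: the secondary model lists nearly all the score's components, although screening decides which survive. Eligibility alone does not make the score complete, because one major criterion admits a patient without the other twelve being assessed; completeness depends on the data collection form. And at both interim looks the DSMB receives only subject ID, PEP, bleeding and group, so a score-adjusted test could not be run on that dataset.

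These points reduce the size of the suggestion. They do not remove it, because a useless score costs almost nothing (0.838 against 0.839) and a useful one helps.

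**Conclusion.** This is a minor efficiency improvement, not an error in the plan. The score is pre-specified and fixed before randomization, yet the primary comparison does not use it, and the one planned adjusted estimate relies on outcome-driven selection.

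The score itself would bring 0 to about 3 percentage points of power, and moving off the conservative Fisher test about 3 more, with type I error near 5%. A 95%-extreme imbalance in the score would move the odds ratio by a factor of about 1.07 to 1.11 at odds ratios of 2 to 3 per point. That is small against a design odds ratio of 0.48 and could matter only for a borderline result. Adjustment would remove only the imbalance that the score captures.

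These figures rest on 1:1 allocation, the design rates, assumed score distributions and assumed odds ratios of 1 to 3 per point. If the true odds ratio is 1.5 or less, the score adds essentially nothing.

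**What to change.** In section F, before unblinding:

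1. Name a single score-adjusted primary analysis, for example a two-sided Mantel-Haenszel test at 0.05 stratified by level of the section F risk score, with sparse levels pooled by a rule written down in advance.
2. Report the standardized risk difference with its confidence interval, so that the result stays on the scale of the difference in proportions.
3. Keep the planned Fisher's exact test as a sensitivity analysis.
4. State that all 13 inclusion criteria are recorded for every randomized patient, not only those that establish eligibility, so that the score is complete.
5. For the looks at 400 and 600 patients, either keep Fisher's test for the interim efficacy comparison or add the score to the DSMB dataset, and say which.

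The cost is a few sentences of wording and slightly more analysis work, with no additional patients. If the form already captures every criterion, no new data are needed. Any adjusted odds ratio is conditional on risk and should be labelled as such beside the standardized risk difference.
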